3 BACKGROUND INFORMATION

3.1 Background

Ovarian cancer is the twelfth leading cause of cancer death in the United States. Based on data from SEER 18 2006-2012, the overall five-year survival rate is 46.2% and for distant and unstaged disease it is only 24-28% (SEER 2016, Kosary 2007). The standard management of primary ovarian cancer is optimal cytoreductive surgery (usually defined as reduction of residual disease to less than 1 to 2 cm) followed by chemotherapy (Al Rawahi 2013). Experts are advocating complete cytoreductive surgery for tumor debulking as it results in better overall survival than optimal cytoreduction (Shih 2010). Although tumor debulking surgery is the cornerstone of current treatment in patients, the lesions can be diffuse and numerous, of various sizes, and often not readily visible in the surgical field, leading to varying rates of optimal cytoreduction among surgeons (Ibeanu 2010). This is an important factor in the poor prognosis for patients with advanced ovarian cancer. Tumor-specific intraoperative fluorescence imaging may improve staging and debulking efforts in cytoreductive surgery.

3.2 Rationale

Over 90% of ovarian epithelial cancers express folate receptor (FR), a folate binding protein, making this receptor an ideal target for marking most ovarian cancers (Markert 2008, Parker 2005, Ross 1994, Toffoli 1998, Weitman 1992). This also makes FR an ideal target for intraoperative imaging of this cancer, facilitating cytoreduction, and potentially improving outcomes in these patients (Kalli 2008). Chemotherapy does not appear to affect FR expression in ovarian cancer specimens as examined by immunohistochemistry (Crane 2012), so prior treatment is unlikely to affect utility of FR α ligands as imaging agents. Since FR α is normally expressed only in the proximal tubules of the kidneys and in the choroidal plexus, uptake of OTL-0038 in the kidneys is possible. However, the fluorescence signal in the kidneys is expected to be significantly lower than the tumor tissues (Ross 1994). A fluorescent probe targeting FR, Folate-FITC (fluorescein isothiocyanate), has been investigated for use in patients with ovarian cancer (van Dam 2011).

While folate will initially distribute to all cells, redistribution, metabolism, and excretion will eliminate most of this agent from healthy tissues within 2-3 hours. Tumor cells that over expresses FR α will retain folate and any fluorescent labeled folate conjugate and internalize this (Leamon 1993). On Target Laboratories, Inc. has developed OTL0038, a folate analog ligand conjugated with an indole cyanine-like green dye as a tumor-imaging agent in patients with tumors that overexpress FR α .

[REDACTED]

[REDACTED]

[REDACTED]

[REDACTED]

3.3 Investigational Product

The resulting imaging agent, OTL0038 (also known as OTL-0038 or OTL-038), is the active pharmaceutical ingredient (API) of the drug product, OTL38 Injection (also known as OTL38). All nonclinical studies were conducted with API (drug substance) while clinical studies were conducted using OTL38 Injection.

[REDACTED]

The safety profile of OTL0038 has been characterized in a comprehensive series of non-human pharmacokinetic and toxicology studies. The results of the OTL0038 Phase 1-enabling nonclinical safety program in rats and dogs demonstrated the safe use of OTL0038 as an intra-operative imaging agent.

[REDACTED]

The data from a Phase 1a study in healthy volunteers supports the safety of OTL38 Injection

[REDACTED]

Recent results from a Phase 2 study demonstrated that OTL38 injection was safe and well-tolerated in patients with FR+ ovarian cancer scheduled to undergo primary surgical cytoreduction, including interval debulking.

[REDACTED]

Please refer to the Investigator's Brochure for more detail information on OTL0038 and OTL38 Injection.

3.4 Risks and Benefits of OTL38

3.4.1 Risks

The issues of possible concerns with the use of the OTL38 imaging systems are:

- Presence of an imaging system in the operating room
- Phototoxicity or thermal damage from the light source
- Nonspecific localization of OTL38
- Failure of OTL38 to bind to receptors
- Fading of the chromophore (photobleaching)
- Inability to excite the dye in OTL38 or to record emission
- Adverse events suggestive of hypersensitivity

[Redacted text block]

[Redacted text block]

[Redacted text block]

[Redacted text block]

[Redacted text block]

[Redacted text block]

3.4.2 Benefits

The potential benefits of OTL38 ovarian cancer imaging are:

- Improved staging of the tumor
- Removal of more lesions
- Added assurance of clean margins to excised tumors.

In a preliminary study by [van Dam et al \(2011\)](#), significantly more lesions were detected by surgeons using Folate-FITC than with visual observation alone (34 vs. 7; $p < 0.001$). Lesions as small as 1 mm could be detected and removed. This resulted in better staging of patients as more lesions could be visualized but, more importantly, it resulted in greater tumor debulking. Since the degree of tumor removal directly affects the prognosis, this was a large potential benefit. This would need to be studied with OTL38. Use of OTL38 would not change the surgeon's option to remove additional tissue because of impressions based on experience, visualization, or tactile senses. The smallest detectable tumor using OTL38 in the phase 2 study [REDACTED] in volume.

4 STUDY OBJECTIVES

4.1 Primary

- To confirm the efficacy of OTL38 in combination with fluorescent light to detect additional Folate Receptor-positive (FR+) ovarian cancer lesions not detected by palpation and visualization under normal light in patients with FR+ ovarian cancer scheduled to undergo primary surgical cytoreduction, interval debulking, or recurrent ovarian cancer surgery

4.2 Secondary

- To estimate the proportion of folate positive ovarian cancer patients in whom all lesions, without regard to evaluable lesion status, detected by fluorescent light only are histologically negative, the patient level False Positive Rate (FPRp)
- To estimate the Sensitivity and False Positive Rate for OTL38 in combination with fluorescent light with respect to the detection of FR+ ovarian cancer lesions confirmed by [REDACTED] pathology
- To assess the safety of using OTL38 and [REDACTED] Imaging System for intraoperative imaging with OTL38

4.3 Exploratory

- [REDACTED]
- [REDACTED]
- [REDACTED]
- [REDACTED]

5 STUDY DESIGN

5.1 Overall Investigation Plan

This is a phase 3, randomized, multi-center, single dose, open label, pivotal study in patients diagnosed with, or with high clinical suspicion of, ovarian cancer scheduled to undergo primary surgical cytoreduction, interval debulking, or recurrent ovarian cancer surgery.

All patients participating in the study are expected to receive OTL38 and undergo normal light evaluation; [REDACTED]

[REDACTED] All patients will first undergo evaluation by normal light and all suspicious lesions identified under normal white light will be recorded as such. Following normal light assessment, but prior to any surgical removal of lesions or the use of fluorescent light imaging, patients will be randomized to either undergo fluorescent imaging or not. Patients randomized to the no fluorescent imaging group receive the usual standard of care and surgery based on normal light assessment only. Patients randomized to the fluorescent imaging group will undergo assessment with fluorescent light imaging prior to and after surgery. The specific randomized allocation ratio of normal light and fluorescent imaging patients to normal light only patients will remain blinded to the Investigators and their staff.

[REDACTED]

Efficacy will be assessed for subjects undergoing both normal light and fluorescent light imaging. All subjects exposed to OTL38, regardless of randomized group assignment, will be followed for safety. The study will consist of a screening period of up to 28 days prior to the scheduled surgery, a diagnosis and treatment period (day of surgery; Day 1), and safety assessment visits on Day 7 (+/-4) and Day 28 (+/-4) after surgery. The study database will be frozen when last patient completes the Day 28 assessment (which will be considered the study completion date); AEs/ADEs judged by the Investigator to be at least possibly related to study drug will continue to be reported regardless of how much time has elapsed since the last exposure to study drug. Long-term follow-up data on [REDACTED] will be collected [REDACTED] after surgery from available patients.

5.1.1 Study Assessments

The assessments for this study are listed in [Section 5.7](#).

5.1.2 Safety assessment

All AEs deemed to be related to OTL38 and of severity graded as mild, moderate or severe will be monitored. The following definitions of severity will be considered in this determination:

- Mild: Awareness of signs or symptoms, but easily tolerated and are of minor irritant type. Symptoms do not require therapy or a medical evaluation; signs and symptoms are transient.
- Moderate: Events introduce a low level of inconvenience or concern to the participant, but are usually improved by simple therapeutic measures; moderate experiences may cause some interference with functioning.
- Severe: Events generally require systemic drug therapy or other treatment; they are usually incapacitating.

Safety assessments will also include changes in labs, vitals, and ECG.

5.2 Eligibility Criteria

5.2.1 Inclusion Criteria

To be considered eligible to participate in this study, a patient must meet all the inclusion criteria listed below:

1. Female patients 18 years of age and older
2. Have a primary diagnosis, or at high clinical suspicion, of primary ovarian cancer (of epithelial type), planned for primary surgical cytoreduction, interval debulking, or have recurrent ovarian cancer, and:
 - Who are scheduled to undergo laparotomy for the debulking surgeryOR
 - Who are scheduled to undergo laparoscopy and pre-authorized to undergo laparotomy for the debulking surgery if cancer is detected on the laparoscopy
3. A negative serum pregnancy test at Screening followed by a negative urine pregnancy test on the day of surgery or day of admission for female patients of childbearing potential
4. Female patients of childbearing potential, or less than 2 years postmenopausal, agree to use an acceptable form of contraception from the time of signing informed consent until 30 days after study completion
5. Ability to understand the requirements of the study, provide written informed consent for participation in the study and authorization of use and disclosure of protected health information, and agree to abide by the study restrictions and to return for the required assessments

5.2.2 Exclusion

Patients will be excluded if they meet any of the exclusion criteria listed below:

1. Previous exposure to OTL38
2. Known FR-negative ovarian cancer
3. Planned surgical debulking via laparoscopy or robotic surgery, with no intent of laparotomy
4. Patients with known ovarian cancer miliary disease determined pre-operatively to be inoperable
5. Any medical condition that in the opinion of the investigators could potentially jeopardize the safety of the patient
6. History of anaphylactic reactions
7. History of allergy to any of the components of OTL38, including folic acid
8. Pregnancy or positive pregnancy test
9. Clinically significant abnormalities on the electrocardiogram (ECG)
10. Presence of any psychological, familial, sociological or geographical condition potentially hampering compliance with the study protocol and follow-up schedule
11. Impaired renal function defined as $eGFR < 50 \text{ mL/min/1.73m}^2$
12. Impaired liver function defined as values $> 3x$ the upper limit of normal (ULN) for alanine aminotransferase (ALT), aspartate aminotransferase (AST), alkaline phosphatase (ALP), or total bilirubin.
13. Known Stage IV ovarian cancer with brain metastases
14. Received an investigational agent in another clinical trial within 30 days prior to surgery
15. Known sensitivity to fluorescent light

5.3 Patient Enrollment

Prior to enrolling patients in the study, Sponsor will require copies of the site's written IRB/IEC approval of the protocol, informed consent forms, and all other applicable material. All patients must provide informed consent before commencement of study-related procedures. All patient who enter the screening period (entry is defined as the point at which the patient signs the informed consent) will receive a unique patient identification number that will be used to identify the patient throughout the clinical study.

The patient identification number must remain constant throughout the entire clinical study; it must not be changed after initial assignment, even if the patient is rescreened. The patient identification number will not necessarily be the same as the randomization number assigned in the study.

A patient will be considered enrolled when the patient signs the informed consent form and receives the study drug.

5.3.1 Randomization

[REDACTED] To achieve this safeguard, a blinded randomization of patients to undergo fluorescent imaging or not will occur after normal light assessment, but prior to surgery or fluorescent imaging. The randomization will be generated from a single centralized randomization list. [REDACTED]

[REDACTED] The randomization date is to be documented in the patients' medical record and on the enrollment electronic case report form (eCRF).

5.4 Patient Discontinuation Criteria

Although a single dose of study drug is infused on Day 1, a patient may be withdrawn from the study for any of the following reasons:

- Request of the patient or patient's representative
- AEs or adverse device effects (ADEs) based on the judgment of the Investigator
- The Investigator decides that it is in the patient's best interest
- The patient is noncompliant with the protocol
- Lost to safety assessments during Visits 3 and 4 ([REDACTED])
- Death
- Other

If a subject is withdrawn at any time, the reason(s) will be recorded on the relevant page of the eCRF.

Patients discontinued due to AEs or ADEs will be monitored until resolution or stability of the event based on the judgment of the investigator.

5.5 Study Drug Information and Dosage

5.5.1 Identification and Description of Test Article

OTL38 will be supplied in vials containing 1.6 mL of solution of 2 mg/mL OTL38 for a total of 3.2 mg of drug per vial.

5.5.2 Packaging and Labeling

The study medication will be packaged in vials and labelled by the Sponsor's clinical supplies designee.

The labels will include:

- Name and contact information for the Sponsor:
On Target Laboratories, Inc,
[REDACTED]
- Route of administration: injection
- Quantity supplied: 3.2 mg OTL38 per vial
- Pharmaceutical dosage form: [REDACTED]
- Storage conditions: keep frozen [REDACTED]
- CAUTION: New Drug – Limited by Federal Law To Investigational Use
- Lot number
- Manufacturing date in day/month/year format.

5.5.3 Storage and Handling of Test Article

Study medication should be stored [REDACTED] and with protection from light (see Site Study Reference Manual).

[REDACTED]

[REDACTED]

5.5.4 Study Drug Administration

OTL38 will be prepared following the Dose Preparation for OTL38 Injection Pharmacy Manual (see [Appendix 1](#)). OTL38 will be administered intravenously over approximately 60 minutes. The infusion will be completed at least one hour prior to intraoperative imaging.

[REDACTED]

[REDACTED]

5.5.5 Camera/Imaging System

The [REDACTED] imaging systems used in this study are not approved for use with OTL38, and are therefore considered investigational for purposes of this study.

5.5.5.1 Summary of the Camera/Imaging System Requirements

[REDACTED]

[REDACTED]

[REDACTED]

[REDACTED]

5.5.5.2 Quality System Requirements

On Target Laboratories outsources design and contract manufacturing for the final device and its labeling, and packaging. As part of the On Target Laboratories Supplier Approval Process, the contract manufacturer’s quality system and compliance with the following federal and international regulations are assessed:

- USA 21 CFR Part 820: Code of Federal Regulations, Quality System Regulations; current edition
- ISO 13485:2003 Medical Devices – Quality management systems – Requirements for regulatory purposes
- Medical Device Directive: Council Directive 93/42/EEC concerning medical devices

5.6 Concomitant Medications

5.6.1 Allowed Medications

Necessary supportive measures for optimal medical care will be given throughout the study. Additional care may be administered as indicated by the treating physician and patient's medical need, and after discussion with the medical monitor.

All concomitant medications and supportive therapy administered starting Day 1 prior to the infusion of OTL38 until Visit 4 must be recorded on the appropriate case report form (eCRF).

5.6.2 Prohibited Medications

No other investigational products will be allowed during this study. If the patient is on any folate supplement (including multi-vitamin supplements or pre-natal vitamins), the patient will need to stop taking the supplement 48 hours before scheduled drug infusion/surgery.

Note that OTL38 should not be mixed with other medicinal products and should not be given simultaneously through the same IV line as another medicine.

5.7 Schedule of Events

5.7.1 Measurement and Evaluations

Please see "[Schedule of Events](#)" for a detailed study schedule, including all measurements and evaluations for the entire study period (Screening to Follow-up) presented in tabular form.

5.7.1.1 Visit 1 (Screening, up to Day -28)

Prior to the initiation of study-specific screening assessments the Investigator or designee must provide the patient(s) a complete explanation of the purpose and evaluations (procedures and assessments) of the study. Subsequently, the patient must sign and receive a copy of an Informed Consent Form and authorization of use and disclosure of protected health information (PHI) that was approved by the institutional review board (IRB). Once informed consent has been obtained, the eligibility of the patient will be determined, and Screening Period assessments will be performed.

- Signed informed consent
- Complete medical history
- Physical examination
- Height and weight

- Concomitant medication assessment
- Vital signs (temperature, blood pressure, and pulse rate)
- Serum Pregnancy test (for women of childbearing potential)
- 12-lead ECG
- Clinical laboratory assessments including hematology, chemistries, and urine analysis

5.7.1.2 Visit 2-Day of Admission (Day 0) or Day of Surgery (Day 1):

- Updated medical history and physical exam
- Concomitant medications assessment
- Urine pregnancy test (for women of childbearing potential)
- [REDACTED]
- Blood samples for PK assessment are to be drawn at the following timepoints,
[REDACTED]
[REDACTED]
- AEs recording including during infusion of OTL38
 - During and post-surgery any AEs and ADEs will be recorded.
- Vital signs (temperature, blood pressure, and pulse rate) will be taken at baseline (15 minutes prior to OTL38 infusion), every 15 minutes during infusion (only blood pressure and pulse rate), and then every hour after infusion until surgery is initiated. During and post-surgery these will be recorded per institutional practice.

5.7.1.2.1 Intra-operative Procedures

- [REDACTED]
- [REDACTED]
- [REDACTED]

- **FOR ALL PATIENTS UNDERGOING FLUORESCENT IMAGING FOLLOW**

[REDACTED]

- [REDACTED]

[REDACTED]	[REDACTED]	[REDACTED]
[REDACTED]	[REDACTED]	[REDACTED]
[REDACTED]	[REDACTED]	[REDACTED]
[REDACTED]	[REDACTED]	[REDACTED]

- [REDACTED]

- [REDACTED]

- [REDACTED]

- [REDACTED]

- [REDACTED]

[REDACTED]

[REDACTED]

[REDACTED]

[REDACTED]

5.7.1.3 Visit 3 (Day 7 [\pm 4]):

- Safety assessments will be scheduled for Day 7 (\pm 4) on site.
- AEs, ADEs, and concomitant medication information will be recorded.
- Physical exam, ECG, clinical laboratory and vital sign assessments will be performed.

5.7.1.4 Visits 4 (Day 28 [\pm 4]):

- Visit 4 will be scheduled for Day 28 (\pm 4) either via patient telephone interview or clinic visit
- AEs, ADEs, and concomitant medication information will be collected.

5.7.1.5 Follow-up

- Follow-up clinic visit will be scheduled for [REDACTED]

5.7.2 Interim Analysis

No interim analysis is planned.

5.7.3 Surgical Reporting Schematic

5.7.4 Post-Surgery Questionnaire

After each surgery, the Investigator will fill out the questionnaire per [Appendix 3E](#).

5.7.5 Pathology Samples

All excised lesions will be processed as outlined in [Section 5.7.1.2.1](#). Please refer to the site Manual for additional details.

5.7.6 Pharmacokinetic Samples

The PK blood samples will be processed to plasma, stored, and shipped appropriately to the indicated bioanalytical laboratory.

6 STUDY ENDPOINTS

6.1 Primary Efficacy

- Proportion of patients with at least one evaluable FR+ ovarian cancer lesion confirmed by [REDACTED] pathology (Standard of truth) that was detected using the combination of OTL38 and fluorescent light but not under normal light or palpation. [REDACTED]

6.2 Secondary Efficacy

- False Positive Rate at the patient level (FPRp) [REDACTED]
- Sensitivity or True Positive Rate (TPR) for OTL38 in combination with fluorescent light, [REDACTED]
- False positive rate (FPR) for OTL38 in combination with fluorescent light, for the purpose of this protocol, [REDACTED]

6.3 Exploratory Efficacy

- █ [REDACTED]
- █ [REDACTED]
- █ [REDACTED]
- █ [REDACTED]
- █ [REDACTED]
- █ [REDACTED]
- █ [REDACTED]
- █ [REDACTED]
- █ [REDACTED]
- █ [REDACTED]
- █ [REDACTED]
- █ [REDACTED]

- [REDACTED]

6.4 Safety

- Incidence rates of treatment-emergent AEs (TEAEs), SAEs, and Adverse Device Effects (ADEs), and changes in clinical laboratory values, vital signs, physical examination, concomitant medications and ECG through Visit 4.

6.5 Pharmacokinetics

- Primary plasma pharmacokinetic (PK) parameters for OTL38, including systemic clearance (CL), volume of distribution of the central and peripheral compartments (V_c , V_p), and distributional clearance(s) (CL_d), on a population and individual patient level.
- Effects of patient specific covariates (e.g. baseline demographics and laboratory value indicators of renal and hepatic function) upon PK parameters, reported as coefficients demonstrating significance at the alpha level of 0.05.

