1 PROTOCOL SYNOPSIS

Study Title	A Phase 3, Randomized, Single dose, Open-Label Study to Investigate the Safety and Efficacy of OTL38 Injection (OTL38) for Intra-operative Imaging of Folate Receptor Positive Ovarian Cancer
Sponsor	On Target Labs, Inc. [REDACTED]
Primary Objectives	
 To confirm the efficacy of OTL38 in combination with fluorescent light to detect additional Folate Receptor-positive (FR+) ovarian cancer lesions not detected by palpation and visualization under normal light in patients with FR+ ovarian cancer scheduled to undergo primary surgical cytoreduction, interval debulking, or recurrent ovarian cancer surgery
Secondary Objectives	
 To estimate the proportion of folate positive ovarian cancer patients in whom all lesions detected by fluorescent light only are histologically negative, the patient level False Positive Rate (FPRp) To estimate the Sensitivity and False Positive Rate for OTL38 in combination with fluorescent light with respect to the detection of FR+ ovarian cancer lesions confirmed by [REDACTED] pathology To assess the safety of using OTL38 and [REDACTED] Imaging System or Quest Spectrum Imaging System for intraoperative imaging [REDACTED]
Exploratory Objectives	
 To estimate the lesion inoperability rate for all lesions identified by fluorescent light only. To describe the diagnostic characteristics of OTL38 in combination with fluorescent light for lesions of various histological and pathological cell types To assess CA-125 levels before and after surgery To estimate the plasma pharmacokinetics (PK) of OTL38 in patients with FR+ ovarian cancer scheduled to undergo primary surgical cytoreduction, [REDACTED]
Study Design	
This is a phase 3, randomized, multi-center, single dose, open label, pivotal study in patients diagnosed with, or with high clinical suspicion of, ovarian cancer scheduled to undergo primary surgical cytoreduction, interval debulking, or recurrent ovarian cancer surgery.
 
[REDACTED]

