------------------------------------	--

Number of Subjects
	
A minimum sample size of 100 evaluable patients is required to evaluate the primary efficacy endpoint. [REDACTED]

Number of Investigator Sites
	
Up to 16 investigational sites (14 in the United States and 2 ex-U.S. [the Netherlands]).

Assessments
	
At specified time points as outlined in the schedule of events, patients will undergo the following procedures: collection of informed consent, medical history, demographics, physical exam including weight, vital signs including temperature, and ECG. Patients will also provide samples for clinical chemistry, CBC with differential, and a serum/urine test for women of child-bearing potential. Concomitant medications and adverse events as reported by the patient will be monitored.
 
Blood samples for PK analysis will be drawn from all subjects at sparse time points (30, 60 and 90 minutes) following the start of OTL38 infusion (see Section 6.5).
 
[REDACTED]

Study Endpoints
	
Primary Efficacy:
 
 Proportion of patients with at least one evaluable FR+ ovarian cancer lesion confirmed by [REDACTED] that was detected using the combination of OTL38 and fluorescent light but not under normal light or palpation. [REDACTED] 
[REDACTED]

	
Secondary Efficacy:
 
• False Positive Rate at the patient level (FPRp) [REDACTED]• Sensitivity or True Positive Rate (TPR) for OTL38 in combination with fluorescent light. [REDACTED]• False positive rate (FPR) for OTL38 in combination with fluorescent light, for the purpose of this protocol. [REDACTED] 
[REDACTED]
 
[REDACTED]
 

[REDACTED]	[REDACTED]	[REDACTED]	

[REDACTED]	[REDACTED]	[REDACTED]	

 
[REDACTED]
	[REDACTED]	[REDACTED]	[REDACTED]	[REDACTED]	[REDACTED]	[REDACTED]
[REDACTED]	[REDACTED]	[REDACTED]					
[REDACTED]	[REDACTED]	[REDACTED]					
	
[REDACTED]
 
[REDACTED]
 
[REDACTED]
 
[REDACTED]
						

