8.2.2 Analysis Sets

The following definitions will be used to derive the analysis sets for the study.

Full Analysis Set (FAS): The FAS for the primary analysis of the primary endpoint will include subjects exposed to OTL38 and randomized to undergo fluorescent imaging (OTL38+Imaging) who:

- Were evaluated under both normal light and fluorescent light imaging, and
- Had [REDACTED] pathology and histology confirmation (positive for FR+ Ovarian Cancer) for at least one lesion detected under normal light or fluorescent light imaging

[REDACTED]

Per Protocol Analysis Set (PPAS): The per protocol analysis set will include all patients meeting the FAS criteria in addition the following criteria:

- Meeting all the inclusion and none of the exclusion criteria
- Having no major protocol deviations

[REDACTED]

Safety Analysis Set (SAS): The safety analysis set will include all patients exposed to OTL38.

[REDACTED]

[REDACTED]

[REDACTED]

[REDACTED]

[REDACTED]

Pharmacokinetic Analysis Set: Every patient receiving a full dose of OTL038 and with one or more measurable drug-plasma concentrations will be included in the PK Analysis Set.

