8.2.6.3 Pharmacokinetics

The pharmacokinetics of OTL38 will be estimated by fitting compartmental pharmacokinetic models to the serial plasma concentration-time (Ct) data using established methods including maximum likelihood parameter estimation and nonlinear mixed-effects (NLME) modeling approaches, with the patient serving as the random effect. Various structural PK and error models will be fit to data using a qualified, standard software package. Primary PK parameters will be estimated at the population level and for individual patients as post-hoc empirical Bayesian estimates (EBEs). The actual primary parameters may vary depending on the supported model, but are likely to include systemic clearance (CL), volumes of distribution of the central and peripheral compartment(s) (V_c , V_p), distributional clearance (CL_d), or derivatives thereof. Inter-patient variability in select PK parameters will be assessed as part of the model, as will the residual error. Secondary parameters may include, but are not limited to: model predicted maximum concentration (C_{max}), time of C_{max} (T_{max}), area under the concentration-time curve (AUC) to the last time point (AUC_{last}) and to infinity (AUC_{inf}), and the terminal elimination half-

life ($T_{1/2}$). The model predicted Ct profiles and observed Ct data will be presented as figures for the population and individual level. Individual primary EBE and secondary parameters will be presented as listings at the patient level.

Potential covariates explaining inter-subject PK variability, and their influence upon PK parameters, will be initially screened using a two-stage approach with standard parametric statistical tests on the individual patient EBEs, focusing on CL. Covariates of interest will include baseline demographic values (e.g. height, weight, age, BSA, BMI, race), and laboratory values predictive of renal or hepatic function (e.g. BUN, creatinine, calculated creatinine clearance or GFR, AST, ALT, alkaline phosphatase, albumin, and total bilirubin). If warranted, a single stage approach with direct incorporation of covariates into the NLME PK model may be undertaken using a forward addition - backward deletion method at an alpha level of 0.05.

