The final model PK parameter estimates, and any bootstrapped results, will be reported as a table, including the estimates, their standard errors, or confidence intervals. The covariate coefficient estimates, their standard errors, and the associated P values for those significant at the alpha level of 0.05 will be tabulated. Relationships between covariates and PK parameters will be graphically presented as figures. Additional details will be found in the PK analysis plan (PKAP).

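### PK covariate effects are reported only if p<0.05, so a non-significant renal or hepatic effect on OTL38 clearance has no clearly promised estimate or interval

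*Protocol*

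**What the plan says.** PK is an exploratory objective in the synopsis: "To estimate the plasma pharmacokinetics (PK) of OTL38 in patients with FR+ ovarian cancer". One of its two endpoints is the effect of patient covariates, including laboratory indicators of renal and hepatic function, on the PK parameters.

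- **Endpoint definition.** Protocol 6.5 has these effects "reported as coefficients demonstrating significance at the alpha level of 0.05", and SAP 12.5 uses the same words. The synopsis gives the endpoint without the significance condition.
- **Coefficient table.** Protocol 8.2.6.3 says of the covariate coefficients, their standard errors and "the associated P values for those significant at the alpha level of 0.05 will be tabulated". SAP 13.3.5 repeats this.
- **How covariates are chosen.** Individual empirical Bayes estimates (EBEs), mainly of CL, are first screened with standard tests. A direct search in the nonlinear mixed-effects (NLME) model is optional and "may be undertaken using a forward addition - backward deletion method at an alpha level of 0.05".
- **Other outputs.** The final-model parameters "will be reported as a table, including the estimates, their standard errors, or confidence intervals". Plots carry no filter: "Relationships between covariates and PK parameters will be graphically presented as figures". Individual EBEs are listed by patient.
- **Who is in the analysis.** Protocol 8.2.2 takes fully dosed patients "with one or more measurable drug-plasma concentrations will be included in the PK Analysis Set".

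Both documents leave further detail to a separate PK analysis plan, which was not available for this review.

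**The concern.** The main question a covariate analysis has to answer is how large an effect the data still allow. A filter on p<0.05 answers only whether the effect was detected. If creatinine clearance or bilirubin misses the threshold, the planned table has no row for it. A reader cannot then tell a precise estimate near zero from an imprecise one that leaves room for a material change in CL.

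The design makes that distinction matter. Per the synopsis, PK samples are taken at 30, 60 and 90 minutes from the start of an infusion that lasts about 60 minutes (Protocol 5.5.4), so individual CL may be poorly resolved. Eligibility removes patients with eGFR below 50 or liver tests above three times the upper limit. This narrows the covariate range and lowers power for the two organ-function groups the endpoint names. Non-significance could therefore be weak evidence of no effect.

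**Working it through.** **1. Does any planned output supply the number?**

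| Output | Filter | Estimate and interval for a non-significant covariate? |
|---|---|---|
| Covariate coefficient table | p<0.05 | No, on the natural reading |
| Final-model parameter table | None stated | Not if the stepwise search at 0.05 is run, because the covariate has been removed |
| Covariate plots | None | Relationship visible; no estimate or interval promised |
| Individual EBE listing | None | Patient values only |
| SAP 7 general convention | None | CIs accompany p-values for hypothesis tests, but only where applicable |
| PK analysis plan | Unknown | Not supplied |

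**2. How often would a true effect go untabulated?** The plan gives no power, effect size or variability for this analysis, so there is no figure to reproduce. The one anchor is "A minimum sample size of 100 evaluable patients is required to evaluate the primary efficacy endpoint". The PK set is defined differently and may be larger, so N=150 is shown as well.

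Assumptions: residual SD of log CL 0.30; slope = change in log CL per covariate SD; rel = share of individual CL variance resolved, 1 or 0.5. The test is a two-sided t test at 0.05 with N-2 degrees of freedom and noncentrality

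slope × √N ÷ (SD ÷ √rel).

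For slope 0.10 and N=100 this is 0.10 × 10 ÷ 0.30 = 3.33 when rel = 1, and 0.10 × 10 ÷ 0.424 = 2.36 when rel = 0.5. Probability of p≥0.05:

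| True change in CL per covariate SD | N=100, rel 1 / 0.5 | N=150, rel 1 / 0.5 |
|---|---|---|
| 5% | 62% / 79% | 47% / 70% |
| 10% | 9% / 35% | 2% / 18% |
| 15% | 0.1% / 6% | 0% / 1% |
| 20% | 0% / 0.3% | 0% / 0% |

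For the 10% change at N=100, varying the SD of CL from 20% to 50% gives 0.1-49% (rel 1) and 6-71% (rel 0.5).

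Cross-check: a separate simulation regressed log CL on log eGFR (SD of log eGFR 0.2, N=100, SD 0.3). A true exponent of 0.5, which is 0.5 × 0.2 = 0.10 per covariate SD, gave 90% power. That is about 10% missed, in line with 9%.

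**3. What would an omitted row have shown?** At N=100 the standard error is 0.30 ÷ 10 = 0.030 (rel 1) or 0.424 ÷ 10 = 0.042 (rel 0.5). An estimate of 0.05 has 95% CI 0.05 ± 1.984 × 0.030 = -0.01 to 0.11, or 0.05 ± 1.984 × 0.0424 = -0.03 to 0.13. It is non-significant and left out, yet compatible with an 11-13% change per covariate SD.

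**4. Are the tabulated coefficients biased?** Two forces act in opposite directions.

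- *Selection.* The mean |estimate| given p<0.05, divided by the truth, is 1.60 / 2.15 (rel 1 / 0.5) for a 5% change, 1.05 / 1.24 for 10%, and 1.00 / 1.03 for 15%. For 20% it is 1.00 at both.
- *Shrinkage.* EBEs from a model without the covariate are pulled to the mean by the factor (slope² + SD²) ÷ (slope² + 2 × SD²) when half the variance is unresolved. This is 0.0925 ÷ 0.1825 = 0.507 (5%), 0.100 ÷ 0.190 = 0.526 (10%), 0.1125 ÷ 0.2025 = 0.556 (15%) and 0.130 ÷ 0.220 = 0.591 (20%).

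The products for rel = 0.5 are 2.15 × 0.507 = 1.09, 1.24 × 0.526 = 0.65, 1.03 × 0.556 = 0.57 and 1.00 × 0.591 = 0.59. Simulation of the EBE regression gives about 1.10, 0.66, 0.58 and 0.59.

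**The case against.** The best defence is that the documents do not consistently impose the filter. The synopsis omits it. The SAP 7 convention attaches confidence intervals to tests with no significance condition. The table sentence can be parsed so that only the P values, and not the estimates and standard errors, are limited to significant covariates. The PK analysis plan is the natural home for a full covariate table.

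Part of this stands. It is why the claim is that no estimate is clearly promised, and why confidence is medium. But the endpoint definitions in Protocol 6.5 and SAP 12.5 attach the condition to the coefficients themselves, which favours the restrictive reading of the table sentence. The SAP 7 convention is qualified and does not mention these analyses. A plan that cannot be seen cannot be relied on to widen an endpoint the protocol has narrowed.

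A second defence is that the impact is small. This largely stands: effects of 15-20% per covariate SD are rarely missed in the base case, and the eligibility limits mean the trial cannot describe frank organ impairment whatever is tabulated. Poor resolution of CL or a larger SD makes the omission more common.

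A reader might go further and infer that the significant coefficients will overstate the true effects. The documents do not support that. The only covariate step certain to run is the EBE screen, and with sparse sampling its shrinkage can offset or reverse the selection effect. Nor are non-significant relationships hidden altogether, because the plots are unfiltered.

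**Conclusion.** The point holds as a reporting weakness. On the natural reading of four sections, a renal or hepatic effect on CL with p≥0.05 gets no tabulated estimate or interval, and no other supplied text clearly provides one.

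In the base case (N=100, SD of CL 30%), this would happen to a true 10% change per covariate SD 9% of the time with well-resolved CL and 35% with half the variance unresolved. It is commoner for smaller effects and rare for larger ones. Every PK value here is an assumption, and the ranges above show how strongly the result depends on them. The net direction of bias in the coefficients that are tabulated is not known.

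Severity is low and confidence medium. The objective is exploratory, and the primary efficacy test is not affected.

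**What to change.** In Protocol 6.5 and 8.2.6.3 and SAP 12.5 and 13.3.5, replace the significance condition on reporting with:

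*Estimates and 95% CIs, from the NLME model, will be tabulated for a short pre-named set of covariates, including at least one renal and one hepatic measure, whatever their p-value.*

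The pre-named covariates should stay in that model and not be open to removal by the stepwise search. Taking the estimates from the NLME model, not from regression on EBEs, also avoids the shrinkage described above. The EBE screen and stepwise search can remain for further covariates, labelled exploratory. The change brings these sections into line with the synopsis, and the PK analysis plan should carry the same rule.

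The cost is wording in two protocol and two SAP sections, with no added blood draw, visit or patient. The NLME covariate step, now optional, becomes required for the named set. The table will be longer, and some of its intervals will be wide.
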